1.1 Objectives

We seek to further examine the biology of chronic venous ulceration. Our rationale for this study is:

1. Can we effectively predict from biological markers in whom standard therapy will not culminate in wound healing?
2. Can potential therapeutic targets be identified?
3. What changes occur in the biological profile of a chronic venous ulcer over various points in time?

Our belief is that the potential benefits of this study to wider healthcare community may be in effectively stratifying patients with chronic venous ulceration by risk of treatment failure. This may allow resources to be concentrated on high risk patients.

In addition, identifying therapeutic targets may in the future reduce the proportion of patients in whom standard treatment fails or ulcers recur.

Study of the same patients over time will help us understand the process of healing in chronic venous ulceration and determine the differences in patients who ultimately heal versus those who do not.

2. Eligibility and Inclusion

- Forty patients to be recruited from Vascular Surgery Clinics at Imperial College NHS Trust, and Cambridge University Hospitals NHS Foundation Trust.
- Male or female over the age of 18 years
- Chronic venous ulceration – Defined as wound of greater than four weeks in duration between the foot and the ankle with an Ankle Brachial Pressure Index greater than 0.85.
- Ulceration present for at least four weeks.
- Colour venous duplex evidence of chronic venous insufficiency showing either reflux or obstruction.

3. Exclusion Criteria

- Acute infection in the studied lower limb within the last four weeks
- History of malignancy in the lower limb to be studied
- History of connective tissue disease

- Patients on medications that can cause immunosuppression – Corticosteroids, chemotherapy or radiotherapy for cancer and recombinant immunological medications.

4. Study Design and Methodology

Forty patients who fulfil the criteria for the study will be recruited from Vascular Surgery clinics in hospitals under the auspices of Imperial NHS Trust in London and Cambridge University Hospitals NHS Foundation Trust in Cambridge.

In summary, this study is a prospective cohort study of patients with venous leg ulceration with samples of blood, urine and venous leg ulcer fluid collected over multiple time points over an initial twenty-week period with standard treatment for leg ulceration. In patients not healed fully at twenty weeks, they will be offered an Urgostart® dressing and further assessments carried out to the end of follow up at twenty-eight weeks.

The study will take place between August 2013 and February 2015.

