4.1 Procedures and Assessments

4.1.1 Initial Assessment

- A full history and examination will be completed.
- Venous severity scoring (4).
- CEAP (Clinical-etiologic-anatomy-pathophysiology) scoring (5).
- Colour venous duplex to establish integrity of the venous system.
- Ankle brachial pressure index.
- Routine blood tests: Full blood count, urea, electrolytes, glucose, glycosylated haemoglobin (if patient suffers from diabetes).
- Assessment of wound healing: This will be performed using digital planimetry by which electronic representations of the ulcer are formed and the area calculated.
- Wound ulcer fluid – Two techniques performed simultaneously.
 1. “Occlusive dressing technique” (6). This technique involves the placement of a clear adherent dressing over the ulcer. After ninety minutes in a seated position. The dressing is pierced with a 21 gauge needle and any accumulated fluid is sampled.
 2. “Filter disc technique” (7). This involves placement of filter discs on top of the ulcer bed separated by a permeable transparent dressing to filter out solid material.
- Urine sampling: A mid-stream urinary sample shall be requested from the patient in a standard specimen pot without additives.
- Special blood tests: A sample shall be taken from the antecubital fossa and placed in a standard bottle without additives.
- The patient's ulcer will be managed using compression bandaging.

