4.3 Proposed Analyses

These assays would be performed on ulcer fluid, urine and blood samples collected at the initial and each subsequent assessment.

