4.3.3 Other First Line Assays

- PAI-1, lactotransferrine, S100A9, Annexine 1, AGEs (advanced glycation end-products)
- Markers of oxidative stress-alantoinuric acid ratio, protein carbonyl content
- Plasminogen activators - uPA, tPA

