4.5 Statistics

Statistical analysis will be performed to analyse the patient recruitments in terms of baseline clinical characteristics. Survival analysis will be used to demonstrate ulcer healing. Biological assays will be analysed using univariate statistical analysis. Metabonomic assay data will be mathematically modelled and analysed using multivariate statistical models.

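### Infection outside the studied leg is neither excluded nor flagged, although serum and urine, two of the three assayed sample types, reflect the whole body

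*Combined protocol and SAP*

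**What the plan says.** Section 3 sets two disease exclusions by body site: "Acute infection in the studied lower limb within the last four weeks" and "History of malignancy in the lower limb to be studied". Two others apply to the whole body: "History of connective tissue disease", and immunosuppressive medication, which covers corticosteroids and "chemotherapy or radiotherapy for cancer and recombinant immunological medications".

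Section 4.3 states the sample types: "These assays would be performed on ulcer fluid, urine and blood samples collected at the initial and each subsequent assessment". Under section 4.1.1 the research blood sample comes from the arm ("A sample shall be taken from the antecubital fossa") and the urine is mid-stream. The first-line panel in section 4.3.3 includes "PAI-1, lactotransferrine, S100A9, Annexine 1, AGEs (advanced glycation end-products"). Section 4.3.4 adds IL1, IL6, TNFα and lipocalin 2, if there is enough sample.

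Section 4.5 says: "Biological assays will be analysed using univariate statistical analysis". It gives multivariate models for the metabonomic data and uses baseline characteristics to describe the recruits. It names no covariate, sample flag, sample exclusion or sensitivity analysis for illness elsewhere.

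On the other side, section 4.1.1 requires a history, an examination and a full blood count at week 0, and section 4.1.2 requires a review of changes in health at each later visit.

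**The concern.** A limb-only infection screen suits ulcer fluid, which is sampled at the wound. It does not suit serum and urine. Several listed markers, such as IL6, TNFα and S100A9, are not specific to an ulcer, and a urinary infection acts directly on one of the fluids being profiled. Under section 3 as written, a patient with a chest infection, a urinary infection or an infected other leg qualifies and supplies week-0 serum and urine.

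Those samples bear on Objective 1 in section 1.1, which asks whether markers can predict failure to heal. They also bear on the search for therapeutic targets in Objective 2, where it matters whether a signal comes from the ulcer. With only 40 patients, a few high values unrelated to the ulcer can hide a real marker. If such values cluster in non-healers, they can suggest a marker of ulcer biology that is not one.

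**Working it through.** **1. Scope check.** Each condition is set against section 3.

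| Condition at week 0 | Excluded by section 3? |
|---|---|
| Acute infection, studied leg, within four weeks | Yes |
| Acute infection, any other site | No |
| Past or present malignancy, studied leg | Yes |
| Cancer elsewhere, on chemotherapy or radiotherapy | Yes, through the medication criterion |
| Cancer elsewhere, not on an excluded treatment | No |

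The infection gap is open. The malignancy gap is narrow.

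**2. Inputs.** The documents give N = 40 with no alpha, power, effect size, SD or healing rate, so there is no figure of the plan's own to reproduce. Everything below is assumed: 24 healed v 16 non-healed; SD 0.8 on the natural-log scale (variance 0.64); true difference 0.8 SD; two-sided 5% Welch test on log values; illness in a share p of patients, multiplying the marker by a factor f of 3, 5 or 10.

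**3. Chance of occurrence.** At p = 5%, 40 × 0.05 = 2 patients are expected, and the chance of at least one is 1 − 0.95^40 = 0.87. At 10%, 4 are expected and the chance is 1 − 0.90^40 = 0.985.

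**4. Noise, with illness equally common in both groups.** Illness adds p(1 − p)(ln f)² to the variance, so relative efficiency = 0.64 / [0.64 + p(1 − p)(ln f)²]. For f = 5, (ln 5)² = 2.590:
- p = 5%: 0.64 / (0.64 + 0.0475 × 2.590) = 0.64 / 0.763 = 0.84
- p = 10%: 0.64 / (0.64 + 0.09 × 2.590) = 0.64 / 0.873 = 0.73

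Simulated power, against about 0.68 with no illness:

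| Rise in marker | 5% ill | 10% ill |
|---|---|---|
| 3-fold | 0.64 | 0.60 |
| 5-fold | 0.60 | 0.54 |
| 10-fold | 0.53 | 0.44 |

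The type I error stays at about 5% here, because equal contamination does not bias the comparison.

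**5. Bias, with illness unequal and no true difference.** The spurious log difference is (p in non-healed − p in healed) × ln f. For 5-fold it is 0.05 × 1.609 = 0.08 at 5% v 10%, and 0.15 × 1.609 = 0.24 at 5% healed v 20% non-healed. Simulated type I error:

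| Rise in marker | 5% v 10% ill | 5% v 20% ill |
|---|---|---|
| 3-fold | 5.4% | about 8% |
| 5-fold | 5.4% | about 11% |
| 10-fold | 5.5% | about 13% |

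**6. Cross-check on other assumptions.** Take 20 v 20 patients, a true difference of 1 SD, a normal approximation, and a 2 SD shift from illness (close to 5-fold here, since 1.609 / 0.8 = 2.0). Power falls from 0.885 to 0.83 at 5% ill and 0.77 at 10% ill. With no true difference, the false-positive rate is 5.9% at 5% v 10% ill and 12.5% at 5% v 20%. The pattern is the same.

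**The case against.** The strongest reply has four parts.

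- **The information is already collected.** History, examination, full blood count and visit-by-visit health review would identify many affected patients. This stands: a reader might infer that illness elsewhere is bound to be read as ulcer biology, and the documents do not support that. What is missing is a stated rule for using the information. A choice of samples to drop that is made after marker values are seen would be weaker than a rule set beforehand.
- **Inflated false positives need a large imbalance.** This stands. No section supports a fourfold difference in illness between the groups, and a twofold difference leaves the error close to nominal. The power loss also rests on assumptions, and the protocol sets no power target that it could breach.
- **Ulcer fluid is the core matrix.** Section 4.3.4 places the baseline comprehensive metabolic profile in ulcer fluid, section 4.3.2 tests wound exudate, and the inflammatory cytokines are second-line. This lowers the weight of the point but does not remove it, because section 4.3 extends the assays to urine and blood at every assessment.
- **For prediction, systemic illness may be legitimate signal.** If ill patients heal more slowly, a serum marker that reflects illness can still predict non-healing in the clinic population. This stands against widening section 3 or dropping these patients from the main analysis. It does not support calling such a marker ulcer-related.

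**Conclusion.** The point holds as a mismatch between the body-site scope of the entry screen and two of the three sample types, with no analysis step to cover it. Infection outside the studied leg is the main gap. Cancer not under an excluded treatment is a lesser one, and it would be wrong to infer that cancer elsewhere generally passes the screen.

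The expected harm is lost precision in serum and urine markers: power of about 0.68 falls to between 0.64 and 0.44 across a 3- to 10-fold rise and 5-10% of patients ill. False discovery is a conditional risk. The type I error is near 5.4% at 5% v 10% ill and reaches 8-13% only at 5% v 20%. Prevalence, size of rise, SD, effect and healed/non-healed split are all assumed. The ulcer-fluid analyses are outside this point.

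**What to change.** Add one field to the initial and follow-up data forms: a per-sample flag for acute infection at any site within four weeks, and for active malignancy. At week 0, base it on the history, examination and full blood count. At later visits, base it on the health review, since section 4.1.2 does not repeat the full blood count. Have it assigned without sight of marker values.

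Then state in section 4.5 that serum and urine marker and metabonomic results will be reported both with all samples and without flagged samples, and that a marker will be called ulcer-related only if it holds without them. Judge this on the estimate and its interval, because the restricted set is smaller (with 4 of 40 flagged, 36 remain at week 0). The all-sample result remains available for prediction under Objective 1.

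The cost is one data field, a short addition to section 4.5 and a slightly smaller sample in the restricted analysis. No change to eligibility, procedures or treatment is needed.

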4.1 Procedures and Assessments

4.1.1 Initial Assessment

- A full history and examination will be completed.
- Venous severity scoring (4).
- CEAP (Clinical-etiologic-anatomy-pathophysiology) scoring (5).
- Colour venous duplex to establish integrity of the venous system.
- Ankle brachial pressure index.
- Routine blood tests: Full blood count, urea, electrolytes, glucose, glycosylated haemoglobin (if patient suffers from diabetes).
- Assessment of wound healing: This will be performed using digital planimetry by which electronic representations of the ulcer are formed and the area calculated.
- Wound ulcer fluid – Two techniques performed simultaneously.
 1. “Occlusive dressing technique” (6). This technique involves the placement of a clear adherent dressing over the ulcer. After ninety minutes in a seated position. The dressing is pierced with a 21 gauge needle and any accumulated fluid is sampled.
 2. “Filter disc technique” (7). This involves placement of filter discs on top of the ulcer bed separated by a permeable transparent dressing to filter out solid material.
- Urine sampling: A mid-stream urinary sample shall be requested from the patient in a standard specimen pot without additives.
- Special blood tests: A sample shall be taken from the antecubital fossa and placed in a standard bottle without additives.
- The patient's ulcer will be managed using compression bandaging.

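### Section 4.5 relates AGEs, other assays and metabolic profiles to healing without adjusting or stratifying for diabetes, although diabetics are eligible and their status is recorded at week 0

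*Combined protocol and SAP*

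**What the plan says.** **Who is enrolled.** Section 2 sets the size: "Forty patients to be recruited from Vascular Surgery Clinics" at two trusts. Section 3 lists four exclusions: recent acute infection in the limb, malignancy in the limb, "History of connective tissue disease", and immunosuppressive medication. Diabetes is not among them.

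**What is collected at week 0.** Section 4.1.1 states "A full history and examination will be completed". Its routine bloods include urea and glucose, and end with "glycosylated haemoglobin (if patient suffers from diabetes"). Only the last item is conditional. Section 4.4.1 has the history and routine bloods recorded on a standard form and the clinical data entered in the database.

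**What is assayed.** Section 4.3.3 lists "AGEs (advanced glycation end-products") among the first-line assays. Section 4.3 applies the assays to ulcer fluid, urine and blood.

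**How it is analysed.** Section 4.5 says "Biological assays will be analysed using univariate statistical analysis" and "Metabonomic assay data will be mathematically modelled and analysed using multivariate statistical models". It also plans an analysis of baseline clinical characteristics, without listing the variables, and a survival analysis of healing. No section names diabetes, HbA1c, glucose or urea as a covariate, stratifier or subgroup in a marker analysis.

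**The concern.** Section 1.1 wants to predict failure of standard therapy from biological markers, to find therapeutic targets, and to learn how patients who heal differ from those who do not. The last of these is an observational contrast, and nothing in the design balances diabetes between the two groups. AGEs are glycation products by name, so glycaemia is an obvious rival explanation for an AGE difference. Blood and urine profiles can likewise reflect a patient's general metabolic state as well as the ulcer.

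If diabetics heal less often and carry higher levels of a marker, that marker will separate healers from non-healers even if it has no role in the ulcer. The harm falls mainly on the search for targets, and on any claim that a marker adds to what the history already shows. Metabolites that move together with glycaemia could also give a false signal the look of a coherent pathway. Modelling many metabolites jointly does not prevent this, because multivariate modelling of the profile is not adjustment for a clinical confounder.

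**Working it through.** There is no figure in the plan to reproduce. The documents give N = 40 but no alpha, effect size, SD, healing rate or diabetes prevalence. Every input below except N is an assumption.

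**Inputs.** 24 healers and 16 non-healers (24 + 16 = 40). Proportion diabetic p_H = 15% in healers and p_N = 25% or 40% in non-healers. Marker higher in diabetics by d = 0.5, 1.0 or 1.5 SD. Within each diabetes stratum the SD is 1 and the marker is unrelated to healing. Two-sided 5% test.

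**Step 1: spurious difference** = d × (p_N − p_H).
- Mildest: 0.5 × (0.25 − 0.15) = 0.05 SD
- Middle: 1.0 × (0.40 − 0.15) = 0.25 SD
- Largest: 1.5 × (0.40 − 0.15) = 0.375 SD

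**Step 2: standard error.** Mixing diabetics and non-diabetics gives a group variance of 1 + d²p(1 − p), so SE = √(V_H/24 + V_N/16).
- Mildest: V_H = 1.032, V_N = 1.047, SE = 0.329, ratio 0.05/0.329 = 0.15
- Middle: V_H = 1.128, V_N = 1.240, SE = 0.353, ratio 0.25/0.353 = 0.71
- Largest: V_H = 1.287, V_N = 1.540, SE = 0.387, ratio 0.375/0.387 = 0.97

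**Step 3: false-positive rate.** The normal approximation P(Z > 1.96 − ratio) + P(Z < −1.96 − ratio) gives about 5%, 11% and 16%. Simulated t-tests (20,000 runs per scenario) agree:

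| Scenario | Spurious difference | Unadjusted | With diabetes status |
|---|---|---|---|
| 0.5 SD, 15% v 25% | 0.05 SD | 5.3% | about 5% |
| 1.0 SD, 15% v 40% | 0.25 SD | 11.1% | 4.8% |
| 1.5 SD, 15% v 40% | 0.375 SD | 16.9% | 4.8% |

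The adjusted column comes from a linear model of the marker on healing and diabetes status.

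**Step 4: a wider grid.** A second simulation let the group sizes vary. It assumed diabetes in 15%, 25% or 35% of 40 patients (6, 10 or 14), non-healing of 30% without diabetes and 30%, 50% or 70% with it, and the same shifts. Unadjusted false-positive rates were:
- 4.4% to 5.9% when diabetes does not affect healing, which is no bias
- 5.5% to 10.6% at 50% non-healing in diabetics
- 6.3% to 29.9% at 70%

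With diabetes status added, the rate was 4.3% to 5.9% in all 27 scenarios. One example: at 25% prevalence and 70% v 30% non-healing, the diabetic share is 0.175/0.400 = 43.75% of non-healers and 0.075/0.600 = 12.5% of healers. A 1 SD shift then gives 0.31 SD of spurious difference, with 14.6% false positives unadjusted and 5.0% adjusted.

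**Step 5: what exclusion of diabetics would cost.** Under the upper assumptions 15% of 24 is 3.6 and 40% of 16 is 6.4, so about 20 healers and 10 non-healers remain. Power of a two-sided 5% t-test falls from 86% to 70% for a true 1 SD difference, and from 68% to 51% for 0.8 SD.

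**The case against.** The best defence is that the data needed for adjustment are already planned, the study is exploratory, and the bias is hypothetical. Much of this stands. The documents do not say that diabetes affects healing here, and without that link there is no bias. For prediction alone, a marker that tracks diabetes may still predict, though it adds little to the history. For change over time within a patient, a stable diabetes status largely cancels. What the defence does not supply is any step in section 4.5 that would detect or remove the confounding if it is present.

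A reader might infer stronger points that the documents do not support:

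- *That metabolic profiles are compared univariately.* Section 4.5 assigns them to multivariate models; only the biological assays are univariate.
- *That glucose and urea enter no analysis.* They are recorded at baseline and may be part of the planned analysis of baseline characteristics. The supportable statement is that no marker-healing analysis names them.
- *That limiting HbA1c to diabetics makes adjustment impossible.* Known diabetes comes from the history, and glucose is listed without restriction. What is lost is sight of undiagnosed diabetes and a long-term glycaemia scale common to all 40 patients. Diabetes status alone restored the nominal error rate in the simulations, which assume that it is recorded correctly.
- *That renal function is an equally established confounder.* Renal impairment is not an exclusion, but no calculation here bears on it.

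**Conclusion.** The concern holds in a limited form. Diabetics are eligible, AGEs are a first-line marker, and neither the univariate nor the multivariate analysis adjusts or stratifies for diabetes. A marker of diabetes could therefore be presented as specific to the ulcer or as a target. For a single marker the excess ranges from nothing to roughly three times the nominal 5% (16.9/5 = 3.4) in the main scenarios, and more only if the link between diabetes and healing is stronger than assumed there. All of this rests on assumed prevalence, healing rates and marker shifts. It shows that the mechanism can matter at this sample size, not that it will occur. The gap is in the wording of section 4.5, not in the list of blood tests. It is worth correcting because the correction is cheap and uses data already collected.

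**What to change.** In section 4.5:

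1. For AGEs and the other biological assays, replace the purely univariate healer v non-healer comparison with a model that includes diabetes status from the week-0 history. Report it beside the unadjusted result.
2. For the multivariate metabolic models, state that each candidate metabolite will be checked for whether its association with healing persists after diabetes status is added.
3. Repeat the analysis without diabetics as a descriptive sensitivity analysis only. It should not decide whether a marker counts as new, because the loss of power would discard real markers.

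No extra HbA1c testing is needed for this. The cost is one degree of freedom in 40 patients, some extra analysis and a short paragraph. With so few patients, further covariates should be added sparingly.

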4.1.2 Subsequent Assessments

- Reassessments of the patient will take place at weeks 1, 2, 4, 8, 12 and 20.
- These will involve reviewing any significant changes in health.
- The ulcer area will be measured using digital planimetry to chart progress of healing.
- Compression bandaging will be continued as per the requirements of the patient.
- Wound fluid, urine and special blood tests will be repeated as described above.

4.1.3 Week Twenty – Special Arrangements

If the ulcer has healed by week 20 then the patient will have completed the study. If the ulcer has not healed, the patient's standard of therapy (compression bandaging) will be complemented by the use of an Urgostart® dressing. This product will be used within its licence.

These patients will be followed up to a total of 28 weeks. Assessments as described above will be repeated at weeks 21, 22, 23, 25 and 28. These assessments will be undertaken to detect changes in the microenvironment of the wound in response to a new treatment.

